1.3. Study Schedule of Activities

Table 1: Study SoA

| Procedure | Screening | Treatment Phase | | | | | | Post-Treatment Follow-up Phase | |
|--|-------------|-----------------|----------|----------------|----------------|-------------------|--|-----------------------------------|--------------------------|
| | | Cycle 1 | | Cycle 2 | Cycle 3 | Subsequent Cycles | EOT/ED (as applicable) | Safety Follow-up | Survival Follow-up Phase |
| Study Day(s) | D-42 to D-1 | D1 | D15 | D1 | D1 | D1 | Within 15 days after last dose of lerociclib | Last dose of lerociclib + 30 days | Every 12 weeks |
| Visit Window (days) | - | - | ± 2 days | ± 2 days | ± 2 days | ± 2 days | - | + 5 days | ± 7 days |
| Informed Consent | X | | | | | | | | |
| IRT Participant Number Assignment (After ICF Signature) | X | | | | | | | | |
| Participant ID Card Distribution | | X | | | | | | | |
| Inclusion/Exclusion Criteria | X | X | | | | | | | |
| Demography | X | | | | | | | | |
| Medical History and Current Medical Conditions (Including Details on Cancer Diagnosis, Extent of Cancer, And Prior Anticancer Therapy) | X | | | | | | | | |
| Current Line of Endocrine Therapy For mBC | X | | | | | | | | |
| Prior Medications Review (Including Prior Antineoplastic Therapy) | X | | | | | | | | |
| Concomitant Medications Review | | X (continuous) | | | | | | X | |
| Physical Examination | X | X ^a | | X ^a | X ^a | X ^a | X | | |
| Height | X | | | | | | | | |
| Body Weight | X | X | | X | X | X | X | | |

| Procedure | Screening | Treatment Phase | | | | | | Post-Treatment Follow-up Phase | |
|--|----------------|--|----------------|----------------|----------------|----------------------------|--|-----------------------------------|--------------------------|
| | | Cycle 1 | | Cycle 2 | Cycle 3 | Subsequent Cycles | EOT/ED (as applicable) | Safety Follow-up | Survival Follow-up Phase |
| Study Day(s) | D-42 to D-1 | D1 | D15 | D1 | D1 | D1 | Within 15 days after last dose of lerociclib | Last dose of lerociclib + 30 days | Every 12 weeks |
| Visit Window (days) | - | - | ± 2 days | ± 2 days | ± 2 days | ± 2 days | - | + 5 days | ± 7 days |
| ECOG PS | X | X | | X | X | X | X | | |
| Clinical Laboratory Tests (Hematology, Clinical Chemistry, Coagulation, Fasting Lipid Panel, and Urinalysis) | X ^b | X ^c | X ^c | X ^c | X ^c | X ^c | X | | |
| Pregnancy Test ^d | X ^b | X | | X | X | X | | | |

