6.5. Dose Modification

6.5.1. Lerociclib

A participant may temporarily discontinue from study treatment with lerociclib for a duration of up to 14 days, for any reason. However, any such temporary discontinuations must be reported to the Medical Monitor. Refer to Section [7.1.2](#) for details.

This protocol allows some alteration from the currently outlined lerociclib dosing schedule, but the maximum daily dose will not exceed 300 mg. Dose adjustments of lerociclib for toxicities are to be made according to the organ system showing the greatest degree of drug-related toxicity. Toxicities will be graded using NCI CTCAE v5.0.

No more than 2 lerociclib dose-level reductions in total are allowed for any participant. Toxicity that requires dose-level reduction more than twice will lead to permanent discontinuation of lerociclib dosing for the individual participant. No lerociclib dose re-escalations are allowed if the dose reduction was due to a lerociclib-related toxicity.

In cases where the relationship to lerociclib is unclear, the Investigator may re-challenge the participant after discussion with the Medical Monitor.

Dose reduction will only be performed if the symptom(s) is (are) related to lerociclib in the opinion of the Investigator and not related to the underlying disease. The dose level reductions below will be utilized for the purpose of lerociclib modifications for toxicities.

Table 5: Lerociclib Dose Modifications

| Dose Level | Lerociclib Dose |
|-----------------------|-----------------------|
| Starting dose | 150 mg BID |
| First dose reduction | 100 mg BID |
| Second dose reduction | 50 mg QAM, 100 mg QPM |

BID = twice daily; QAM = once every morning; QPM = once every evening.

An off-drug period of up to 14 days is permitted to allow recovery from any toxicity in order to meet the continuation criteria.

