6.5.1.1. Dose Modifications for Hematologic Toxicity

Table 6: Lerociclib Dose Modifications for Hematologic Toxicity

| Grade of Hematologic Toxicity (per NCI CTCAE v5.0) ^a | Lerociclib Dose Adjustment |
|--|---|
| Grade 3 (any Grade 3 hematologic toxicity except those listed below) | Continue lerociclib and repeat CBC at next scheduled visit or within 7 days. No dose reduction required. Starting at Cycle 5 Day 1, participants with stable Grade 3 neutropenia may have the frequency of CBC monitoring reduced to a different frequency determined by Investigator, if approved by the Medical Monitor. |
| Grade ≥ 3 neutropenia (ANC ≥ 500 to $< 1000/\text{mm}^3$) associated with a documented infection or fever $\geq 38.5^\circ\text{C}$ or Grade ≥ 3 thrombocytopenia (platelets $< 50,000$ to $25,000/\text{mm}^3$) associated with bleeding | Withhold lerociclib and monitor counts weekly until ANC $\geq 1 \times 10^9/\text{L}$ OR platelet count $\geq 75 \times 10^9/\text{L}$ with no further bleeding. Resume therapy at the next lower dose. If no further dose reduction is possible (participant is already receiving the lowest dose), lerociclib treatment must be discontinued. |
| Grade 4 | Withhold lerociclib until the hematological toxicity has recovered to Grade ≤ 2 . Resume therapy at the next lower dose. If no further dose reduction is possible (participant is already receiving the lowest dose), lerociclib treatment must be discontinued. |

^a. Applies to all hematologic adverse reactions, except lymphopenia (unless associated with clinical events, eg, opportunistic infections).

ANC = absolute neutrophil count; CBC = complete blood count; NCI CTCAE v5.0 = National Cancer Institute Common Terminology Criteria for Adverse Events, version 5.0.

The optimal treatment for IMP-induced neutropenia is to withhold lerociclib. Granulocyte colony-stimulating factor will not work in this setting because lerociclib induces a G₁ cell cycle arrest that cannot be overcome by G-CSF. Withholding lerociclib treatment will allow neutrophils to recover naturally.

Neutrophil counts should increase as the lerociclib concentrations in the body decline and the neutrophils are released from G₁ arrest.

If the participant experiences neutropenia lasting more than 10 days after the cessation of lerociclib, and the Investigator believes that G-CSF use is clinically indicated, then the Investigator must contact the Medical Monitor to discuss the use of G-CSF for that participant.

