6.5.1.2. Dose Modifications for Non-hematologic Toxicity

For any non-hematologic toxicity of Grade ≥ 3 severity that persists despite optimal medical treatment, withhold treatment with lerociclib until symptoms resolve to Grade ≤ 2 severity (if not considered a safety risk for the participant). If the treatment interruption duration is > 14 days, approval from the Medical Monitor will be needed to resume treatment.

Treatment should be resumed at the next-lower dose level of lerociclib. If no further dose reduction is possible (participant is already receiving the lowest dose), lerociclib treatment must be discontinued.

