7.1.2. Temporary Discontinuation of a Participant from Study Treatment

A participant may temporarily discontinue from study treatment for a duration of up to 14 days, for any reason. However, any such temporary discontinuations must be reported to the Medical Monitor and study assessments must continue as specified in the SoA.

If the IMP (lerociclib) is temporarily discontinued for any study participant, it may be restarted within the aforementioned 14-day period under the discretion of the Investigator with notice to the Medical Monitor. Beyond a duration of 14 days, the participant may not re-start lerociclib therapy and will be removed from the study.

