4.10.1.3 Visit Windows

Analysis visit windows will be created based on the schedule of assessments in the protocol (Appendix 6.1) as shown below. Any visits outside the visit window will be considered “Unscheduled” and not summarized at a scheduled visit. If multiple records are mapped to the same visit, the one closest to the date of the scheduled assessment will be used. If there is an equal distance from the date of the scheduled assessment, the latest record will be used.

| Visit | Study Day Window |
|------------------|--|
| Screening | [-42, -1] |
| Cycle 1 Day 1 | 1 |
| Cycle 1 Day 15 | [13, 17] |
| Cycle 2 Day 1 | [27, 31] |
| ... | [expected day – 2 days, expected day + 2 days] |
| EOT/ED | [last dose day, last dose + 15 days] |
| Safety Follow-up | [last dose + 25 days, last dose + 35 days] |

For tumor evaluations, the following windows will be implemented:

| Visit | Study Day Window |
|---|--|
| Screening | [-42, -1] |
| Cycle 3 Day 1 | [50, 64] |
| Every 2 cycles (8 weeks) during first 12 months and every 3 cycles thereafter (12 weeks) until EOT/ED | [expected day – 7 days, expected day + 7 days] |
| EOT/ED | [last dose day, last dose + 15 days] |

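### EOT/ED visits that follow a full or extended lerociclib hold can fall outside the 15-day window and drop out of the by-visit end-of-treatment summaries

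*Protocol*

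**What the plan says.** **Visit timing.** Protocol Table 1 places EOT/ED "Within 15 days after last dose of lerociclib" and gives no additional visit tolerance. No other text offers a different anchor, such as the date of the decision to stop. SAP 4.10.1.3 sets the matching analysis window to "last dose day, last dose + 15 days". A visit outside its window is relabelled as unscheduled and "not summarized at a scheduled visit". The next window, Safety Follow-up, is "last dose + 25 days, last dose + 35 days".

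**Holds.** Protocol 6.5.1 states: "An off-drug period of up to 14 days is permitted to allow recovery from any toxicity". The rules for longer holds do not agree:
- Protocol 7.1.2: "Beyond a duration of 14 days, the participant may not re-start lerociclib therapy and will be removed from the study".
- Protocol 6.5.1.2, for non-hematologic toxicity: "If the treatment interruption duration is > 14 days, approval from the Medical Monitor will be needed to resume treatment".
- Protocol Table 6, for Grade 4 hematologic toxicity, gives no time limit of its own: "Withhold lerociclib until the hematological toxicity has recovered to Grade ≤ 2".

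**How EOT values are to be reported.** Protocol 9.3.3.1 bases the by-visit summaries of vital signs, ECGs and laboratory tests on nominal visits. SAP 4.2.1 defines End of Treatment as the value obtained at the EOT visit, and allows an earlier value only where none was collected there. SAP 4.13 states that the protocol's statistical methods were not changed.

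**The concern.** When a hold turns into a permanent stop, the last dose already lies in the past by the length of the hold, and the 15 days have been running throughout. Someone who stops at a scan showing progression will usually still be dosing and has close to the full 15 days. Someone whose toxicity has not recovered after a full hold has almost none.

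EOT/ED is the last scheduled collection of laboratory tests, vital signs, ECG, ECOG status and PROs; Table 1 schedules none of these at Safety Follow-up. Substitutes may be old. Routine ECGs end at Cycle 5 apart from EOT/ED, and cycle visits are 28 days apart, so a 14-day hold may contain none. At stake is whether the by-visit EOT rows represent participants who stopped for toxicity, in a study whose primary objective is safety and tolerability.

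**Working it through.** **Inputs.** Let L be the day of the last lerociclib dose. The EOT/ED window is L+0 to L+15 (Protocol Table 1; SAP 4.10.1.3). Safety Follow-up is L+25 to L+35 (SAP 4.10.1.3). A full permitted hold is 14 days (Protocol 6.5.1, 7.1.2). The SAP row does not name the drug; I read it as lerociclib because those windows are built on the protocol schedule. Visit lags of 3 and 7 days after the decision, and an extended hold of 21 days, are my assumptions.

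**Step 1: days left.** Days left = 15 − (day of decision − L). Each possible visit is then classified by the SAP windows.

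| Decision | Days left | Visit same day | 3 days later | 7 days later |
|---|---|---|---|---|
| L+0 | 15 | EOT/ED | EOT/ED | EOT/ED |
| L+7 | 8 | EOT/ED | EOT/ED | EOT/ED (L+14) |
| L+10 | 5 | EOT/ED | EOT/ED (L+13) | Unscheduled (L+17) |
| L+14 | 1 | EOT/ED | Unscheduled (L+17) | Unscheduled (L+21) |
| L+15 | 0 | EOT/ED | Unscheduled (L+18) | Unscheduled (L+22) |
| L+16 | −1 | Unscheduled | Unscheduled (L+19) | Unscheduled (L+23) |
| L+21 | −6 | Unscheduled | Unscheduled (L+24) | Safety Follow-up (L+28) |

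L+14 is the end of a full hold. L+15 is the first day beyond it, when the 7.1.2 removal rule applies. L+16 and later can arise only if a hold continues past 14 days, as 6.5.1.2 contemplates, or if the decision is delayed.

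**Step 2: the gap.** L+16 to L+24 (24 − 16 + 1 = 9 days) belongs to neither post-dose visit. A visit there is unscheduled unless it happens to fall in a cycle Day 1 window, in which case it is labelled as that cycle. An EOT/ED visit at L+25 or later is labelled Safety Follow-up.

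**Step 3: set against the other definitions.** Take an EOT/ED visit held at L+17.
- Protocol 9.3.3.1: nominally EOT/ED, so its laboratory, vital-sign and ECG values belong in that row.
- SAP 4.2.1: its values are the End of Treatment values, because they were obtained at the EOT visit. The earlier-value fallback does not strictly apply, since a value was collected.
- SAP 4.10.1.3: unscheduled and outside the EOT/ED row.

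SAP 4.9.3 invokes the windows explicitly for laboratory by-visit summaries. For vital signs, ECG and PROs the general wording of 4.10.1.3 applies.

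**Step 4: effect of re-anchoring.** If the same 15 days ran from the decision, the window would close at 14 + 15 = L+29 or 15 + 15 = L+30. That leaves 15 usable days instead of 1 or 0. Both dates lie inside L+25 to L+35, so precedence must be stated.

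**Step 5: how many.** The documents give neither the share stopping for an adverse event nor the share of those stopping after a long hold. For scale only, assume 5% to 20% of 50 per line and a quarter to a half of those. The result is 50 × 0.05 × 0.25 = 0.6 to 50 × 0.20 × 0.50 = 5 per line exposed to the short window. That is not a count of missed windows, since L+14 and L+15 are still in time.

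**The case against.** **The rule can be met.** The permitted hold is one day shorter than the window and its end is known in advance, so a site can hold the visit on L+14 or L+15. This stands: a reader might infer that the rule is impossible to meet after a full hold, and it is not. It is tight. The already-closed case depends on 6.5.1.2 and 7.1.2, which contradict each other.

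**The data are not lost.** A reader might infer loss, but the documents do not support it. All laboratory data are listed, and unscheduled values enter the worst post-baseline laboratory summaries (SAP 4.9.3). QTcF grades are also summarised over any timepoint (SAP 4.9.4), and unscheduled scans count for PFS (SAP 4.10.3.2). AEs are collected to 30 days after the last study intervention dose whether or not EOT/ED is held, so the primary endpoint is untouched. This stands in full. It does not cover the by-visit EOT rows. The PRO proportions improved or worsened are by visit (SAP 4.11.2.1), with no rule bringing in unscheduled values.

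**The row may still be filled.** Scheduled assessments continue during a hold, and Table 6 requires weekly counts for some cytopenias. A value between L+0 and L+15 can be windowed to EOT/ED. This also stands, but such a value displaces the one obtained at the EOT visit.

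**The direction of bias is unknown.** It is tempting to say that the EOT rows would look better than the truth. Nothing shows this. A value taken three weeks off drug reflects longer washout, and an in-window or fallback value closer to exposure could look worse. For ECG, parameters are recorded only when the overall assessment is abnormal and clinically significant (SAP 4.9.4), so no complete quantitative EOT row exists for anyone.

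**Conclusion.** The concern holds as a reporting defect in secondary safety and PRO displays. After a full hold the EOT/ED window has 1 day left, 0 at day 15, and it has closed if an extended hold ends in a stop. A later visit is dropped from, or mislabelled in, the by-visit summaries under a rule that disagrees with Protocol 9.3.3.1 and SAP 4.2.1. Exposure to the rule is selective, because it depends on stopping after toxicity that did not resolve.

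The day counts are exact, given the last lerociclib dose as anchor. How often visits fall late depends on site scheduling and on which long-hold rule operates. The number of participants cannot be derived from the documents, and no percentage of EOT rows should be quoted as a finding. The change is worth making because it costs little and removes an outcome-related exclusion.

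**What to change.** 1. **SAP 4.10.1.3.** Assign EOT/ED by the recorded (nominal) EOT/ED visit and report days since last lerociclib dose beside the EOT summaries. State which label takes precedence when that visit falls within L+25 to L+35. This restores agreement with Protocol 9.3.3.1 and SAP 4.2.1.
2. **Protocol Table 1.** For participants who stop while on hold, time EOT/ED from the decision to discontinue permanently, with the same precedence rule for overlap with Safety Follow-up.
3. **Protocol 6.5.1.2 and 7.1.2.** Reconcile the two statements on holds longer than 14 days. Which rule should govern is a clinical decision for the sponsor and is not proposed here.

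**Cost.** One SAP table row with a precedence sentence, one schedule cell, and a reconciliation already needed. No visit or test is added; items 1 and 2 alter no dosing or stopping rule. The downside is that some EOT values will be taken longer after the last dose, so timing relative to exposure is less uniform; the reported interval makes that visible.

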| FSH Measurement (Female Participants of Non-Childbearing Potential Only) | X | | | | | | | | |
| 12-Lead ECG ^e | X ^b | X | X | X | X | X (at Cycles 4 and 5 only) | X | | |
| ECHO or MUGA with EF | | As clinically indicated by Investigator | | | | | | | |
| Vital Signs | X | X | X | X | X | X | X | | |
| PK Sampling ^f | | X | X | X | X | X (at Cycles 4 and 5 only) | | | |
| Tumor Evaluation (per RECIST v1.1) | X | Every 8 weeks (± 7 days) during the first 12 months and every 12 weeks (± 7 days) thereafter until disease progression, death, withdrawal of consent, loss to follow-up, or participant/legally acceptable representative decision, and at EOT/ED (as applicable). If PR/CR is reported, confirmation of response is required; confirmatory assessment should be performed ≥ 4 weeks after response is first documented. ¹ | | | | | | | |
| Whole-Body Bone Scan ^g | X | Every 8 weeks (± 7 days) for the first 12 months, then: -If initial bone scan is positive for bony lesion, every 12 weeks thereafter, OR -If initial bone scan is negative for bony lesion, bone scan can be done annually or per Investigator standard of care. | | | | | | | |

| Procedure | Screening | Treatment Phase | | | | | | Post-Treatment Follow-up Phase | |
|---|--|--|--|----------|----------|-------------------|--|-----------------------------------|--------------------------|
| | | Cycle 1 | | Cycle 2 | Cycle 3 | Subsequent Cycles | EOT/ED (as applicable) | Safety Follow-up | Survival Follow-up Phase |
| Study Day(s) | D-42 to D-1 | D1 | D15 | D1 | D1 | D1 | Within 15 days after last dose of lerociclib | Last dose of lerociclib + 30 days | Every 12 weeks |
| Visit Window (days) | - | - | ± 2 days | ± 2 days | ± 2 days | ± 2 days | - | + 5 days | ± 7 days |
| Lerociclib Administration/Accountability | | Twice daily continuously in 28-day cycles ^a | | | | | | | |
| Letrozole Administration ⁱ | | Once daily continuously in 28-day cycles | | | | | | | |
| Fulvestrant Administration ⁱ | | X | X | X | X | X | | | |
| Goserelin Administration ^j | X (goserelin dosing required for ≥ 28 days prior to study entry) | X (determined as date of participant's last goserelin dose + 28 days ^l) | q28d after goserelin C1D1 for the individual participant | | | | | | |
| AE/SAE Review | X (continuous from Screening through 30 days after last study intervention dose) | | | | | | | | |

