- f. Predose and postdose blood samples for lerociclib concentration measurement are to be collected prior to and following the dose of lerociclib on Day 1 and Day 15 of Cycle 1, and on Day 1 of Cycles 2, 3, 4, and 5. The postdose blood sample can be collected between 2 hours and 6 hours (\pm 10 minutes) after the administration of lerociclib. It is important to record the actual time of collection. If the participant is due for a 2- or 6-hour 12-lead ECG assessment, the PK sample may be drawn at the same timepoint but should be obtained after the ECG.
- g. Radionuclide bone scans shall be performed at Screening for all participants every 8 weeks (\pm 7 days) for the first 12 months and every 12 weeks thereafter if initial bone scan is positive for bony lesion. If initial bone scan is negative for bony lesion, bone scan should be done annually or as clinically indicated per Investigator standard of care. All participants with a CR must have a radionuclide bone scan as part of confirmation of the CR. Additional bone scans may be obtained at the discretion of the Investigator, if clinically indicated. Participants with bone-only disease may be followed only with bone scans at the discretion of the Investigator. If CT or bone scan have been done for regular clinical care within 28 days before receiving the first dose of lerociclib, these may be used as baseline scans.
- h. Subsequent cycles may be postponed up to 14 days due to lerociclib interruption. Note that subsequent cycles should start on the original schedule (ie first dosing date).
- i. Participants in the 1L and 2L populations will receive the Investigator's choice of letrozole 2.5 mg daily or fulvestrant 500 mg (dosed according to schedule specified in the protocol).

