6.1. Study Intervention(s) Administered

All study participants will receive lerociclib (referred to herein as the IMP) every 28 days (± 2 days), and will also receive Investigator's choice of either letrozole or fulvestrant (referred to herein as NIMPs).

All premenopausal or perimenopausal female participants, and all male participants, must be receiving goserelin for at least 28 days prior to entering the study and will remain on goserelin throughout the study, in accordance with the prescribing information and according to the study site's standard practice. The schedule for administration of goserelin for each individual participant is decoupled from the rest of the study visit schedule, and will be determined by the date of the participant's most recent dose of goserelin at the time of study entry (with "goserelin C1D1" defined as the date of the participant's most recent dose + 28 days, then every 28 days subsequently).

Details of the study interventions are provided in [Table 4](#).

Table 4: Study Intervention(s) Administered

| Intervention Label | Lerociclib | Letrozole | Fulvestrant | Goserelin |
|---------------------------------|--|--|---|--|
| Intervention Name | Lerociclib | Letrozole | Fulvestrant | ZOLADEX (goserelin acetate implant) – for pre- or perimenopausal female study participants and male participants |
| Intervention Description | Tablet taken orally, 50 mg or 150 mg, BID or as indicated in Section 6.5 | Tablet taken orally, 2.5 mg, QD | 500 mg, intramuscular injection, Q2W for initial 3 doses, then Q4W thereafter | Subcutaneous implant, 3.6 mg, Q4W |
| Type | Drug | Drug | Drug | Drug |
| Dosage Formulation | Tablet | Tablet | Solution | Implant |
| Unit Dose Strength(s) | 50 mg, 150 mg | 2.5 mg | 50 mg/mL | 3.6 mg |
| Dosage Level(s) | Starting dose: 150 mg BID or as indicated in Section 6.5 | 2.5 mg QD | Initial dose: 500 mg Q2W (Week 1 Day 1, Week 3 Day 1, Week 5 Day 1) Maintenance dose: 500 mg Q4W | 3.6 mg Q4W |
| Route of Administration | Oral | Oral | Intramuscular | Subcutaneous |
| Use | Experimental | Background intervention | Background intervention | Background intervention |
| IMP or NIMP | IMP | NIMP | NIMP | NIMP |
| Manufacturer | EQRx International, Inc. | STADApHarm GmbH and G Pharma Specialities Limited (ex-US) and Accord Healthcare (US) | EVER Neuro Pharma GmbH (ex-US) and Nanjing King-Friend Biochemical Pharmaceutical Co., Ltd. (US) | AstraZeneca AB (ex-US) and TerSera Therapeutics (US) |

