6.5.2. Letrozole, Fulvestrant, and Goserelin

Dose modification of letrozole, fulvestrant, or goserelin is not allowed during the study for any participant.

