All participants with a CR must have a radionuclide bone scan as part of confirmation of the CR. Additional bone scans may be obtained at the discretion of the Investigator, if clinically indicated. Participants with bone-only disease may be followed only with bone scans at the discretion of the Investigator. If CT or bone scan have been done for regular clinical care within 28 days before receiving the first dose of lerociclib, these may be used as baseline scans.

- h. Subsequent cycles may be postponed up to 14 days due to lerociclib interruption.
- i. Participants in the 1L and 2L populations will receive the Investigator's choice of letrozole 2.5 mg daily or fulvestrant 500 mg (dosed according to schedule specified in the protocol).
- j. All premenopausal or perimenopausal female participants, and all male participants, must be receiving goserelin for at least 28 days prior to entering the study and will remain on goserelin throughout the study, in accordance with the prescribing information and according to the study site's standard practice. For all study participants (female or male) receiving goserelin, their treatment with goserelin must start at least 28 days before their first dose of lerociclib.
- k. After the Safety Follow-up Visit, survival follow-up should be attempted every 12 weeks for each participant in the long-term Survival Follow-up Phase. Follow-up can be performed via telephone, clinic visits, or by receiving information from a family member or another provider who is administering care. Any anticancer therapies used will be collected where possible.
- l. CT or MRI scans obtained prior to informed consent will not need to be repeated if performed within 28 days prior to dosing with lerociclib.

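### Protocol footnote h both postpones cycles after a lerociclib interruption and holds them to the original calendar, so fulvestrant timing and the SAP visit windows have no single governing schedule

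*Protocol*

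**What the plan says.** **Cycle timing.** Protocol Section 1.3 sets lerociclib as "Twice daily continuously in 28-day cycles". Footnote h reads: "Subsequent cycles may be postponed up to 14 days due to lerociclib interruption. Note that subsequent cycles should start on the original schedule", and explains the original schedule as the first dosing date. The SAP's copy, footnote h in Section 6.1, has only "Subsequent cycles may be postponed up to 14 days due to lerociclib interruption".

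**Fulvestrant.** The SoA row "Fulvestrant Administration" is marked at Cycle 1 Day 1, Cycle 1 Day 15 and Day 1 of every later cycle. Footnote i refers its dosing to the schedule given in the protocol, which is Table 4 in Section 6.1: "500 mg, intramuscular injection, Q2W for initial 3 doses, then Q4W thereafter", with the first three doses at Weeks 1, 3 and 5. Table 4 does not mention postponed cycles. Footnote j decouples goserelin from the visit schedule and leaves every other activity on the SoA. Section 6.5.2 says: "Dose modification of letrozole, fulvestrant, or goserelin is not allowed during the study for any participant". It does not say whether a delay counts as a modification.

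**Analysis.** SAP Section 4.2.1 anchors Study Day to first lerociclib exposure. Section 4.10.1.3 sets visit windows at the expected day ± 2 and treats anything outside as Unscheduled, not summarized at a scheduled visit. Section 4.9.3 applies those windows to by-visit laboratory summaries.

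**The concern.** The two sentences of footnote h have the same subject, subsequent cycles, and on their face give different start dates. The situation can arise in any participant: Sections 6.5.1 and 7.1.2 allow lerociclib to be stopped for up to 14 days for any reason, and Table 6 requires holds for some hematologic toxicity.

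Two things are at stake. First, sites can time the background endocrine therapy differently after the same lerociclib hold, and a site that moves fulvestrant with the cycle follows the SoA but departs from Table 4. Second, the SAP permits a postponed cycle in its own schedule while its windows assume that none occurs. Visits from participants with interruptions can therefore drop out of the by-visit tables, in a study whose primary objective is safety and tolerability.

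**Working it through.** **Inputs.** Cycle length 28 days (SoA lerociclib row); maximum postponement 14 days (footnote h); fulvestrant visits (SoA row); fulvestrant schedule (Table 4); window of expected day ± 2 (SAP 4.10.1.3).

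**1. Reproduce the plan's own figures.** Day 1 of Cycle x = 1 + 28(x − 1). For Cycle 2 this is 1 + 28 = 29, and ± 2 gives [27, 31], the window printed in the SAP. The SoA fulvestrant days are 1, 15, 29, 57, 85, 113, 141, 169, with intervals 14, 14, 28, 28 and so on. Weeks 1, 3 and 5 in Table 4 are Days 1, 15 and 29. With no interruption, the SoA and Table 4 agree.

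**2. Apply one 14-day postponement, with fulvestrant kept on Cycle Day 1.** Three readings are possible: (A) the affected cycle and all later ones shift; (B) only the affected cycle shifts, then the original dates resume; (C) no shift.

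| Cycle affected | Reading | Fulvestrant days | Intervals |
|---|---|---|---|
| 2 | A | 1, 15, 43, 71, 99 | 14, 28, 28, 28 |
| 2 | B | 1, 15, 43, 57, 85 | 14, 28, 14, 28 |
| 3 | A | 1, 15, 29, 71, 99 | 14, 14, 42, 28 |
| 3 | B | 1, 15, 29, 71, 85 | 14, 14, 42, 14 |
| any | C | 1, 15, 29, 57, 85 | 14, 14, 28, 28 |

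From Cycle 3 on, the interval to the affected dose is 28 days without a shift and up to 28 + 14 = 42 with one. At Cycle 2 Day 1, the third initial dose, it is 14 days without a shift and up to 14 + 14 = 28 with one. These are nominal intervals, before the ± 2-day visit window.

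**3. Count injections by Day 168.**
- Fixed calendar: Days 1, 15, 29, 57, 85, 113, 141 = 7.
- One 14-day postponement at Cycle 2, carried forward: Days 1, 15, 43, 71, 99, 127, 155 = 7.
- One at Cycle 3, carried forward: Days 1, 15, 29, 71, 99, 127, 155 = 7.
- Two, at Cycles 2 and 3, carried forward: Days 1, 15, 43, 85, 113, 141 = 6.

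**4. Apply the SAP windows.** Cycle 5 Day 1 is expected on Day 1 + 28 × 4 = 113, window [111, 115]. Postponed by 14 days, it falls on Day 127. Cycle 6 Day 1 is expected on Day 141, window [139, 143]. Day 127 lies in neither, so the visit is Unscheduled. A 3-day postponement (Day 116) already misses [111, 115], and no shift up to 14 days reaches [139, 143]. If the shift carries forward, the next Day 1 visits fall on Days 155 and 183 and miss their windows too.

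**5. Cycle-day labels.** SAP 4.2.1 counts cycle days (CXDY) from the first lerociclib day in the cycle. If lerociclib resumes on Day 127, CXDY calls that day Cycle 5 Day 1, while the visit table calls it Unscheduled.

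**The case against.** The strongest reply is that fulvestrant does not depend on footnote h. In the SAP's schedule that footnote is attached to the lerociclib row. The fulvestrant row carries footnote i, which leads to Table 4, where the maintenance interval is 28 days whichever sentence of footnote h is followed. The closing reference to the first dosing date can also be read as a qualification: lerociclib may restart late, but cycles stay on their dates. Section 7.1.2 fits this, since assessments continue per the SoA during an interruption.

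Much of this stands. A reader might infer that the documents offer 28 and 42 days as equal alternatives. They do not: 42 days arises only if a site puts the SoA cycle day above Table 4. But the reply does not settle the matter, because footnote h speaks of cycles, the SoA places fulvestrant on Cycle Day 1, and footnote j keeps every non-goserelin activity on the SoA.

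Other stronger readings also fail:
- The 28 ± 2 days in Section 6.1 ("All study participants will receive lerociclib (referred to herein as the IMP) every 28 days (± 2 days") concerns lerociclib and sets no fulvestrant tolerance.
- The SAP's shorter footnote need not show a different intent. The SAP schedule lags protocol Version 3.0 elsewhere, for example on pregnancy testing and goserelin.
- A reader might infer confounded efficacy and tolerability results. The study is single-arm and descriptive, with no formal comparison, so that is too strong.
- The share of participants affected is not given. Table 6 continues dosing through uncomplicated Grade 3 hematologic toxicity, and Section 4.3 reports no interruptions for Grade 3 neutropenia without fever, so holds may be uncommon.
- The laboratory loss is limited to by-visit tables. SAP 4.9.3 keeps unscheduled values in across-visit summaries such as worst post-baseline value.

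**Conclusion.** The inconsistency is real and should be resolved. Footnote h is at least ambiguous and contradictory on its face, no text ranks its sentences, and the SAP carries only one of them. If fulvestrant moves with a postponed cycle, the interval to that dose is up to 42 instead of 28 days from Cycle 3 on, or up to 28 instead of 14 days at Cycle 2 Day 1, and departs from Table 4. The effect on dose count is small: none by Day 168 for a single postponement, and one injection fewer (6 against 7) for two maximal postponements at Cycles 2 and 3.

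The firmer consequence is in the analysis. A Day 1 visit postponed by 3 to 14 days leaves the by-visit laboratory summaries, and only participants with interruptions are affected. The interval figures assume that fulvestrant is kept on Cycle Day 1; the window result assumes that the visit moves with the cycle. How often either happens cannot be derived from the documents. No view is taken here on which schedule is clinically right.

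**What to change.** The sponsor should reconcile footnote h, the SoA fulvestrant row with footnote i, Table 4, Section 6.5.2 and SAP 6.1 footnote h into one stated rule. The rule should say which calendar fulvestrant follows after a lerociclib interruption; that is the sponsor's clinical decision.

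The SAP should then follow the same rule in three places:
- the Section 4.10.1.3 windows, so that validly postponed cycle visits are not dropped;
- the CXDY definition in Section 4.2.1;
- the fulvestrant planned-dose denominator in Section 4.8, which already allows for prescribed interruptions and modifications but does not say whether a postponed cycle is one.

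Report, by line of therapy, the number of fulvestrant doses given outside their scheduled window. Judge the initial 14-day intervals against their own schedule: a blanket count of intervals outside 28 ± 2 days would flag both planned initial intervals in every fulvestrant participant.

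The cost is a short protocol clarification, matching SAP wording and one exposure row from administration dates already recorded.
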